Statistical Methods: A 3+3 dose escalation design will be used. The maximum tolerated dose will be exceeded if 2 or more patients out of 6 (or a third or more) experience a dose limiting toxicity (DLT) at that dose. The dose immediately below will be recommended for further study. DLTs are defined as any acute toxicity of Grade 4 nausea, Grade 4 skin toxicity, Grade 3+ liver toxicity (metabolic or ascites), or Grade 3+ enteritis. Severe late toxicities of interest (occurring beyond the 4 week period of evaluation and up to 12 months after RT) will include any Grade 3+ gastrointestinal toxicity (such as small bowel ulcer, stricture, perforation, bleed, liver damage, pancreatitis, or cholecystitis). If the rate of any severe late toxicity of interest exceeds 25% (i.e., 7 or more patients in the expanded cohort of 18 treated at the MTD), the study committee will suspend accrual and determine whether further dose modifications are needed; the protocol will be amended accordingly.

TABLE OF CONTENTS

SCHEMA	ii
1. OBJECTIVES	1
1.1. Primary Objectives	1
1.2. Secondary Objectives	1
2. BACKGROUND	1
2.1 Unresectable carcinoma of the pancreas	1
2.2 Rationale	1
3. PATIENT SELECTION	3
3.1 Eligibility Criteria	3
3.2 Exclusion Criteria	3
3.3 Inclusion of Women and Minorities	4
4. TREATMENT PLAN	4
4.1 Radiation Therapy dose escalation	4
4.2 Measuring Health Related Quality of Life	4
4.3 Definition of Dose-Limiting Toxicity	5
4.4 General Concomitant Medication and Supportive Care Guidelines	7
4.5 Duration of Therapy	7
4.6 Duration of Follow Up	8
4.7 Criteria for Removal from Study	8
5. RADIATION THERAPY GUIDELINES	8
5.1 Treatment related planning procedures	8
5.2 RT planning parameters	8
5.3 RT Treatment	10
6. ADVERSE EVENTS	10
7. STUDY CALENDAR	133
8. MEASUREMENT OF EFFECT	144
8.1 Antitumor Effect – Solid Tumors	144
9. STATISTICAL CONSIDERATIONS	155
9.1 Study Design/Endpoints	155
9.2 Sample Size/Accrual Rate	166
9.3 Analysis of Secondary Endpoints	166
10. CONFIDENTIALITY	166
10.1 Patient confidentiality issue	17
REFERENCES	18
APPENDIX A	20
APPENDIX B	21
APPENDIX C	22
APPENDIX D	23

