2. BACKGROUND

2.1 Unresectable Carcinoma of the Pancreas

Cancers involving the upper gastrointestinal tract often present at advanced stages. While surgical resection offers some potential for long-term disease control, few patients present when disease can be addressed with a successful resection. As such, many patients with this disease have an overall survival that is less than one year after diagnosis. Because these cancers may progress both locally and distantly, and cause significant symptoms, patients are candidates to receive a combination of local Radiation Therapy (RT) and systemic chemotherapy. For patients with non-metastatic pancreatic cancer, data support the use of 5-Fluorouracil and RT as a means to favorably impact overall survival (Moertel, 1981). Typically, RT is given concurrently with radiosensitizing chemotherapy using conventional fraction sizes (1.8-2 Gy/fraction), over 5-6 weeks of treatment. Fewer data are available to support the use of RT for carcinoma of ampulla. However, it is known that these cancers are aggressive and have high rates of recurrence after surgical resection (Carter, 2008). In the unresectable setting, whether patients present with locally advanced or metastatic disease, lack of treatment may result in local symptoms including pain, gastrointestinal or biliary obstruction, bleeding, or perforation. For patients who are candidates to receive therapy, RT may be a useful adjunct to systemic chemotherapy to palliate patients of these symptoms (Boz, 2001).

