4.3 Definition of Dose-Limiting Toxicity

The evaluation period of acute toxicity will be defined by the period of 28 days following the first fraction of RT. Dose Limiting Toxicity (DLT) will be defined according to Common Toxicity Criteria version 3.0 (See Appendix B) and includes the following acute toxicities:

- Grade 4 nausea (life-threatening consequences)
- Grade 4 skin toxicity (necrosis or ulceration of full thickness dermis, spontaneous bleeding from involved site)
- Grade 3+ liver toxicity including symptomatic ascites requiring invasive procedure, or total bilirubin $>3 \times$ ULN, or AST $>5 \times$ ULN, or ALT $>5 \times$ ULN that persists until day 28, and is attributable to radiation therapy.
- Grade 3+ enteritis (abdominal pain, fever, change in bowel habits with ileus, peritoneal signs) that is attributable to radiation therapy.

Patients must have a minimum of 3 weeks of follow-up after RT start for patient data to contribute enough follow-up for consideration of dose-limiting toxicity. However, any DLT that occurs with shorter follow-up will count towards the dose escalation rules. In addition, any grade 5 toxicity (i.e., death) considered possibly, probably or likely related to RT will be considered a DLT.

Any late toxicity that occurs beyond the 4 week period of evaluation will be closely followed and documented as a toxicity of interest. Included are the following severe late toxicities of RT:

- Grade 3+ gastrointestinal ulcer, fistula, stricture, or perforation (symptomatic and severely altered GI function, IV fluids or TPN ≥ 24 hrs, intervention indicated)
- Grade 3+ gastrointestinal mucositis (confluent ulcerations or pseudomembranes, bleeding with minor trauma)
- Grade 3+ gastrointestinal bleed (transfusion, interventional radiology or endoscopic or operative intervention)
- Grade 3+ gastrointestinal necrosis (inability to aliment adequately by GI tract, interventional radiology, intervention indicated)
- Grade 3+ liver toxicity including symptomatic ascites requiring invasive procedure, or total bilirubin $>3 \times$ ULN, or AST $>5 \times$ ULN, or ALT $>5 \times$ ULN, or asterixis, that is attributable to radiation therapy.

- Grade 3+ enteritis (abdominal pain, fever, change in bowel habits with ileus, peritoneal signs) that is attributable to radiation therapy.
- Grade 3+ pancreatitis (interventional radiology or operative intervention indicated)

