- Grade 3+ cholecystitis (interventional radiology or operative intervention indicated)

These severe, late toxicities will be evaluated between 1 and 12 months of therapy. There is no minimum follow-up time after RT start required for patient data to contribute enough follow-up for toxicities of interest.

Enrollment of 12 additional toxicity-evaluable patients at the MTD will provide a cohort of 18 patients at the putative MTD. If six or fewer of the 18 patients experience a toxicity of interest during the evaluation period, the combination will be considered tolerable. If 7 or more patients experience a toxicity of interest, the study committee will suspend accrual and determine whether further dose modifications are needed; the protocol will be amended accordingly. If the true probability of DLT at the MTD is 50%, the combination will be identified as too toxic with probability 0.88. If the true probability of DLT at the MTD is 25%, the combination will be identified as having an acceptable toxicity profile with probability 0.86.

Management associated with the above adverse events is outlined in Section 7.

Dose escalation will proceed within each cohort according to the following scheme. Dose-limiting toxicity (DLT) is defined above.

Number of Patients with DLT at a Given Dose Level	Escalation Decision Rule
0 out of 3	Enter 3 patients at the next dose level
≥ 2	Dose escalation will be stopped. This dose level will be declared the maximally administered dose (highest dose administered). Three (3) additional patients will be entered at the next lowest dose level if only 3 patients were treated previously at that dose.
1 out of 3	Enter at least 3 more patients at this dose level. 
 • If 0 of these 3 patients experience DLT, proceed to the next dose level. • If 1 or more of this group suffer DLT, then dose escalation is stopped, and this dose is declared the maximally administered dose. Three (3) additional patients will be entered at the next lowest dose level if only 3 patients were treated previously at that dose.
≤ 1 out of 6 at highest dose level below the maximally administered dose	This is generally the recommended phase 2 dose. At least 6 patients must be entered at the recommended phase 2 dose.

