6. ADVERSE EVENTS

Adverse event (AE) monitoring and reporting will be performed.

- Radiation side effects are limited to the area involved in the treatment field. Acute and late toxicity related to radiation therapy may include fatigue, nausea and vomiting, skin erythema, subcutaneous fibrosis, esophagitis, pericarditis, diarrhea, myelitis, damage to the small bowel (including stricture or obstruction, bleed, fistula formation, or perforation), liver dysfunction, kidney damage, and radiation enteritis.
- Acute toxicity including Grade 4 nausea, Grade 4 skin toxicity, and Grade 3 liver toxicity will be referred to as dose limiting toxicities (DLT).
- Late toxicity including any Grade 3+ GI toxicity (small bowel damage including stricture or obstruction, bleed, fistula formation, or perforation; liver damage including ascites but not including abnormal lab values only; pancreatitis, cholecystitis) will be considered a toxicity of interest.
- All life-threatening Grade 4 and all fatal toxicities (Grade 5) must be reported immediately and evaluated.

- Acute toxicity: Acute side effects are considered as occurring \leq 28 days from the start of radiation therapy. They will be documented using the NCI Common Terminology Criteria for Adverse Events (CTCAE) version 3.0 (A copy can be downloaded from <http://ctep.info.nih.gov>). The relevant sections are included in the appendix.
- Late toxicity: Late side effects are considered as occurring $>$ 28 days from the start of radiation therapy through a 12 month total evaluation period. They will also be documented using the NCI Common Terminology Criteria for Adverse Events (CTCAE) version 3.0. The relevant sections are included in the appendix.
- University of Chicago Reporting Guidelines
 - If the reaction requires reporting, the Research Nurse or MD reports the adverse reaction to the Cancer Clinical Trials Office (CCTO) at [contact] by the end of the business day when he/she becomes aware of the event. Events occurring after business hours will be reported to the CCTO by 12 pm (noon) the next business day.
 - The following information is required when calling in the event:
 - Caller's Name and Telephone Number
 - Patient Initials
 - Patient Medical Record Number
 - IRB Protocol Number
 - PI of Study
 - Attending Physician
 - Date of Event
 - Description of Event (including grade of the event and attribution of the event and if the event required hospitalization)

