 - E-mail is sent to the research nurse, attending physician and PI of the study informing them that adverse reaction notification has been received.
 - The University of Chicago's IRB Serious Adverse Event Form must be sent to the CCTO within **5 calendar days of event occurrence**. The UC IRB Serious Adverse Event form is available on-line at: <http://ors.bsd.uchicago.edu/HS/newirbforms>. This form must be typed. Once the forms are completed, the original is forwarded to the study PI to review and sign. The signed report is delivered to the QA Coordinator. A weekly report of delinquent or pending documents will be forwarded to the applicable person who reported the event. All delinquent reporting (greater than 10 days from event occurrence) must include documentation of reason for delinquency and may require implementation of an action plan.
 - Once the appropriate AE documents have been received, the CCTO forwards these to the IRB. A copy will be forwarded to the appropriate Research Nurse.
- Data Safety and Monitoring

- Data Safety and Monitoring will occur at the weekly University of Chicago GI oncology phase I/II conference meetings, which are lead by senior level medical oncologists. At each meeting, all active studies will be reviewed for safety and progress toward completion. Toxicities and adverse events will be reviewed at each meeting and a Data Safety and Monitoring form will be completed for each protocol and signed by either the Principal Investigator, the Chairman of the Department or by his designate if the Chairman is not available.

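### The 7-of-18 late-toxicity rule counts an RT-related death the same as a Grade 3 event, so a dose can be called tolerable with two or more such deaths

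*Combined protocol and SAP*

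**What the plan says.** Section 4.3 sets a 28-day acute window and lists the acute DLTs. It then adds that "any grade 5 toxicity (i.e., death) considered possibly, probably or likely related to RT will be considered a DLT". The next paragraph turns to later events: "Any late toxicity that occurs beyond the 4 week period of evaluation will be closely followed and documented as a toxicity of interest". The late list that follows is Grade 3 or worse throughout. Appendix B gives Grade 5 as death for the clinical categories; only the laboratory rows (AST/ALT and bilirubin) have no Grade 5.

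The late events feed one numeric rule. Seven or more patients of 18 suspend accrual for study committee review. Otherwise "If six or fewer of the 18 patients experience a toxicity of interest during the evaluation period, the combination will be considered tolerable". The Schema gives the same boundary: "If the rate of any severe late toxicity of interest exceeds 25% (i.e., 7 or more patients in the expanded cohort of 18". Neither place mentions the grade of the events.

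Section 6 provides the oversight. "All life-threatening Grade 4 and all fatal toxicities (Grade 5) must be reported immediately and evaluated", and at the weekly conference "Toxicities and adverse events will be reviewed at each meeting and a Data Safety and Monitoring form will be completed for each protocol". No count and no required action is attached to a late death in either provision.

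**The concern.** A tolerability conclusion that pools Grades 3, 4 and 5 treats an endoscopic intervention and a fatal perforation as equal evidence. For acute toxicity the protocol does not do this: it singles out an RT-related death as a DLT even though death is not on the acute list. The late rule has no counterpart, yet it governs months 1 to 12, most of the follow-up. Ulceration, stricture and perforation are the late effects that Section 2.2 reports for pancreatic SBRT.

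What is at stake is the final statement about the dose. The plan can be followed exactly and report a dose as tolerable with two or more RT-related deaths. Whether those deaths alter the conclusion then depends on case-by-case judgment that the plan does not require before the label is applied.

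**Working it through.** **1. The plan's own figures.** With n = 18 and a boundary of 7 (Section 4.3), exact binomial:

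- P(X ≥ 7 | p = 0.50) = 0.881 (stated 0.88).
- P(X ≤ 6 | p = 0.25) = 0.861 (stated 0.86).

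Both reproduce. They depend only on how many patients have an event, not on its grade.

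**2. What two deaths mean.** 2/18 = 11.1%. The Clopper-Pearson 95% limits are the 0.025 quantile of Beta(2, 17) and the 0.975 quantile of Beta(3, 16): 1.4% and 34.7%.

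**3. How often deaths and the label coincide.** Let d be the RT-death risk to month 12 and t the total risk of a Grade 3+ event including death, with all 18 followed to month 12 or death and each death counted as one event. Then

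P(deaths ≥ 2 and events ≤ 6) = Σ (x = 2 to 6) C(18, x) t^x (1 − t)^(18 − x) · P(Bin(x, d/t) ≥ 2).

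The values of d are assumptions. The two values of t come from the documents: about 10% (Section 2.2, for a different regimen, a single 25 Gy fraction) and 25% (the Schema limit).

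| d | P(≥ 2 deaths in 18) | joint, t = 10% | fatal share d/t | joint, t = 25% | fatal share d/t |
|---|---|---|---|---|---|
| 1% | 0.014 | 0.014 | 10% | 0.009 | 4% |
| 2% | 0.050 | 0.049 | 20% | 0.033 | 8% |
| 3% | 0.100 | 0.100 | 30% | 0.068 | 12% |
| 5% | 0.227 | 0.225 | 50% | 0.162 | 20% |

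Dividing each joint value by P(≥ 2 deaths): given two or more deaths, the count still reads tolerable in about 99% of trials at t = 10% and in 65% to 71% at t = 25%. The 99% is nearly automatic, since two deaths supply only two of the seven events needed.

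**4. What the DLT rules would catch.** If a late RT death is a DLT, two such deaths among the 3 or 6 escalation patients at a level stop escalation. Suppose exactly two deaths occur in the 18, fall at random, and there are no other DLTs. Both fall among the first six with probability C(6,2)/C(18,2) = 15/153 = 0.10. Otherwise at least one is in the 12 expansion patients, for whom the 3+3 table has no decision row. The joint probabilities in step 3 consider the 7-of-18 count alone and do not deduct these cases.

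**5. Operating characteristics of a trigger at two deaths.** In 18 patients it fires with the probabilities in the second column of the table. Applied separately to levels of 3, 3 and 18 patients, the probability is 1 − P(X ≤ 1 of 3)² · P(X ≤ 1 of 18) = 0.014, 0.052, 0.105 and 0.238 at d = 1%, 2%, 3% and 5%.

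Other thresholds in 18 patients: one death fires in 0.30 of trials at d = 2%. Three deaths fire in 0.005 at d = 2%, but in only 0.058 at d = 5%, against 0.227 for two.

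**6. Misattributed disease deaths.** Take a true RT-death risk of 2% and add 1, 3 or 5 percentage points (assumed) for disease deaths called possibly RT-related. P(≥ 2 of 18) at 3%, 5% and 7% is 0.10, 0.23 and 0.36.

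**7. Timing.** A simulation with accrual of 1 to 2 patients per month (Section 9.2), one-month waits between cohorts and death times uniform over 12 months fires before the last enrolment in 1.0% to 2.4% of trials at d = 2% and in 6% to 12% at d = 5%.

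**The case against.** The strongest case against is that deaths are already handled. Section 6 review starts at the first death, not the second, and the Grade 5 clause in 4.3 carries no time limit, so read plainly it makes a late RT death a DLT. The committee review proposed here resembles what exists, and its threshold is a matter of taste. The disease also mimics the toxicity: Section 2.1 says that "lack of treatment may result in local symptoms including pain, gastrointestinal or biliary obstruction, bleeding, or perforation". A trigger that accepts possibly related deaths therefore cannot separate a true 5% RT-death risk from a 2% risk plus 3 points of misattribution; both give 0.23 in 18 patients.

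Much of this stands, and it rules out three stronger inferences that a reader might draw.

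- *Late deaths go unmonitored.* They do not; Section 6 covers them. What it lacks is any link to the tolerable label.
- *Section 4.3 excludes a late death from the DLTs.* The Schema and Section 6 do describe DLTs as acute ("Acute toxicity including Grade 4 nausea, Grade 4 skin toxicity, and Grade 3 liver toxicity will be referred to as dose limiting toxicities (DLT"), which leans that way. But recording a late death as a toxicity of interest does not stop it from also being a DLT. This is a wording gap, not a contradiction.
- *The plan would accept six RT deaths in 18.* That needs the narrow reading of the Grade 5 clause. On the plain reading six of 18 is a third, and the Schema and Section 9.1 say that a third or more with a DLT exceeds the MTD. Two to five deaths can remain inside the tolerable result on either reading, unless enough of them fall among the escalation patients to stop the dose there.

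What does not stand is that existing review makes the change redundant. Section 4.3 states a conclusion, and nothing in Section 6 suspends it.

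**Conclusion.** The point holds as a cheap improvement to a decision rule; it is not an error in the calculation. As written, a dose with six or fewer late events is considered tolerable even when two or more are RT-related deaths.

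The size is uncertain. No RT-death rate is given in the documents. At assumed risks of 1% to 2% the situation arises in about 1% to 5% of trials. The larger values at 3% and 5% with a 10% total require 30% and 50% of severe events to be fatal, which is a strong assumption. The figures also assume complete follow-up to month 12 or death.

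A death-specific rule would mainly change the final tolerability conclusion. It would seldom stop accrual early, because most late deaths would come after the last patient is enrolled. The threshold of two is a judgment: one death would prompt too many reviews, and three would rarely respond.

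**What to change.** Leave the Grade 5 clause in Section 4.3 as it is, so that an RT-related death at any time remains a DLT and still counts in the 3+3 rules for its level. Limiting that clause to 28 days would be less protective: two late RT deaths at a level of 3 or 6 patients are at least two DLTs and stop escalation under the literal text.

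After the 7-of-18 rule, add:

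*Independently of this count, if 2 or more patients at a dose level have a Grade 5 event that meets the attribution standard of the Grade 5 clause, between first fraction and month 12, accrual at that level and above is suspended for study committee review. The review records the attribution of each death, and the dose is not declared tolerable until it is complete.*

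Print the trigger probabilities beside the rule.

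The cost is a short amendment, with no extra patients, visits or data. At a true 2% RT-death risk an unneeded review occurs in about 5% of trials. That rises to about 10% to 36% in 18 patients if 1 to 5 further points of disease deaths are called possibly RT-related, which is why the review should record attribution. The rule requires a review; it does not reject the dose.

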9.2 Sample Size/Accrual Rate

The study will accrue 18 patients at the putative maximum tolerated dose, giving a sample size of up to 24 patients. Accrual will likely be 1-2 patients per month. Toxicities of interest that occur within the 1-12 month time frame after RT start will be documented. For further detail regarding modification of enrollment or dose escalation based on late toxicities of interest, see section 5.2.

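### The late-toxicity rule suspends accrual only at a fixed 7 events, so at the planned accrual rate it often fires after all 18 MTD patients are enrolled; it needs a boundary by number enrolled.

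*Combined protocol and SAP*

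**What the plan says.** Section 4.3 builds the late-toxicity cohort from six escalation patients plus twelve more: "Enrollment of 12 additional toxicity-evaluable patients at the MTD will provide a cohort of 18 patients at the putative MTD". Two outcomes are defined. The favourable one is: "If six or fewer of the 18 patients experience a toxicity of interest during the evaluation period, the combination will be considered tolerable". The unfavourable one is: "If 7 or more patients experience a toxicity of interest, the study committee will suspend accrual and determine whether further dose modifications are needed". The synopsis repeats the count of 7 in 18.

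On timing, section 4.3 says: "These severe, late toxicities will be evaluated between 1 and 12 months of therapy". It adds: "There is no minimum follow-up time after RT start required for patient data to contribute enough follow-up for toxicities of interest". Section 9.2 says: "Accrual will likely be 1-2 patients per month".

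On performance, section 4.3 says: "If the true probability of DLT at the MTD is 50%, the combination will be identified as too toxic with probability 0.88". It gives 0.86 as the chance of an acceptable finding when the true rate is 25%. Both statements name DLT, although the rule they describe counts late toxicities of interest; they are read here as referring to the latter.

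No interim look, hold for late follow-up or lower threshold for a part-enrolled cohort appears anywhere. Section 9.2 refers to section 5.2 for enrolment changes based on late toxicity, but section 5.2 covers radiotherapy planning and contains no such rule. Section 6 requires weekly safety review and immediate reporting of life-threatening Grade 4 and fatal events, without a numerical late-toxicity threshold.

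**The concern.** Suspending accrual protects patients only while some remain to be enrolled. Here the endpoint takes up to 12 months to appear, and 18 consecutive patients can be enrolled in 8.5 to 17 months. A fixed count of 7 also ignores the denominator: read literally, 6 of 6 calls for no suspension, and neither does 6 of 18.

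The plan reports no probability of stopping before accrual is complete. Someone reading 0.88 beside the words about suspending accrual could take it for that probability. At stake is how many patients receive a dose with a high rate of severe late gastrointestinal toxicity before a written rule calls for a pause.

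**Working it through.** **1. Reproduce the plan's figures.** With X binomial, n = 18:
- P(X ≥ 7 | p = 0.50) = 0.881, stated as 0.88.
- P(X ≤ 6 | p = 0.25) = 0.861, stated as 0.86.

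Both are correct. Both assume that all 18 outcomes are complete, so time does not enter.

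**2. Accrual time.** From the first to the 18th patient there are 17 intervals: 17/1 = 17 months at 1 per month, 17/2 = 8.5 months at 2 per month (pauses ignored).

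**3. Events seen when patient 18 starts (by hand).** Take evenly spaced entry and onset uniform over months 1-12. A patient with f months of follow-up has shown a share min(max(f − 1, 0), 11)/11 of the eventual risk.
- 1 per month: f = 0, 1, …, 17. The shares sum to (1 + 2 + … + 10)/11 + 6 = 5 + 6 = 11. Expected events = 0.5 × 11 = 5.5.
- 2 per month: f = 0, 0.5, …, 8.5. The shares sum to (0.5 + 1.0 + … + 7.5)/11 = 60/11 = 5.45. Expected events = 0.5 × 5.45 = 2.7.

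Both are below the trigger of 7.

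**4. Simulation of the rule as written.** From the documents: 18 patients, trigger 7, 1-2 per month, window of months 1-12, true rate 50%. Assumed: Poisson accrual; 28-day holds after MTD patients 3 and 6, matching the DLT window; no deaths; onset either uniform, or front-loaded with mean 3 months after month 1. At least 8,000 trials were run per setting.

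| 50% true rate | 1/month | 1.5/month | 2/month |
|---|---|---|---|
| P(7th event before 18th enrolment), uniform | 0.27 | 0.10 | 0.03 |
| Same, front-loaded | 0.53 | 0.37 | 0.22 |
| Expected events at 18th enrolment, uniform | 5.3 | 4.1 | 3.1 |
| Same, front-loaded | 6.6 | 5.8 | 5.1 |
| Mean patients not enrolled because of the rule, uniform | 0.8 | 0.2 | 0.1 |
| Same, front-loaded | 1.9 | 1.1 | 0.7 |

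Front-loaded probabilities move by about 0.02 with the way the onset curve is cut at month 12. When the rule fires early, about 15-16 patients are already enrolled. Inserting a higher-dose cohort of 3 or 6 patients before MTD patients 4-6 changes the probabilities by 0.01 or less.

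**5. Boundary by number enrolled.** Suspend at max(3, 7n/18 rounded up) events with n enrolled. Since 7×7/18 = 2.7, 7×8/18 = 3.1, 7×11/18 = 4.3, 7×13/18 = 5.1 and 7×16/18 = 6.2, the limits are 3, 4, 5, 6 and 7 events, with steps at n = 8, 11, 13 and 16.

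| 50% true rate | 1/month | 1.5/month | 2/month |
|---|---|---|---|
| P(suspend before 18th enrolment), uniform | 0.42 | 0.18 | 0.07 |
| Same, front-loaded | 0.72 | 0.56 | 0.39 |

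Model variants give values up to 0.45, 0.22 and 0.09 (uniform) and 0.74, 0.58 and 0.45 (front-loaded). About 9-12 patients are enrolled when the boundary fires early. At a 25% true rate, the chance of never suspending is about 0.84-0.86 (uniform) or 0.80-0.83 (front-loaded), against 0.86 for the fixed rule.

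**The case against.** The best defence is that this is a classification rule for the completed cohort. The 0.88 is worded as the chance of identifying the dose as too toxic, not of stopping accrual, and the synopsis ties the count to the cohort of 18. That stands: the figures are right for that use, and a late trigger still determines whether the dose is called tolerable, which protects later patients. What remains is that the written action is to suspend accrual, and its chance of happening in time is not given.

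A reader might go further and infer that the rule cannot act in time or protects almost no one. The documents do not support that. They contain no onset distribution, and at 1 per month with early onset the rule fires in time in about half of trials and keeps nearly two patients from enrolling. With a 60% true rate at 1 per month and evenly spaced accrual, the seventh event precedes patient 18 in 53-81% of the trials that reach seven.

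A reader might also add deaths to make the timing look worse. With an assumed median survival of 9 months and uniform onset, average survival to onset is about 0.62, so observed toxicity is 0.5 × 0.62 = 31%. That mixes fewer events with late timing and no longer describes a 50% observed rate, so it is not used here.

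The weekly review could pause accrual by judgement at any time, so six of six would hardly pass unnoticed. This is partial mitigation, since no criterion is written. Finally, the proposed boundary also divides by patients with little follow-up and gains little at 2 per month with uniform onset. That is true, and it is a limit of any 12-month endpoint under fast accrual.

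**Conclusion.** The point holds as a design weakness, not an arithmetic error. At the plan's own 50% toxic rate, the only numerical late-toxicity rule suspends accrual before the 18th enrolment in about 3-27% of trials with uniform onset and 22-53% with front-loaded onset, across 1-2 patients per month. The 0.88 and 0.86 reproduce and should stay, labelled as classification probabilities. The size depends on the assumed onset curve and on accrual speed; the weakness is greatest at 1.5-2 per month with later onset and modest at 1 per month with early onset. The change is worth making because it is cheap, but its benefit is uneven.

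**What to change.** Keep 7 of 18 as the final classification. In section 4.3, add an accrual-suspension boundary by number enrolled at the MTD, checked at the existing weekly review:

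| Enrolled at the MTD | Suspend accrual at (patients with a toxicity of interest) |
|---|---|
| up to 7 | 3 |
| 8-10 | 4 |
| 11-12 | 5 |
| 13-15 | 6 |
| 16-18 | 7 |

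Label 0.88 as the chance of ever reaching 7 with complete follow-up, and report beside it the chance of suspending before full accrual over a range of onset assumptions. Correct the pointer in section 9.2 so that it leads to this rule.

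The cost is a five-line table and a short simulation; no new meeting is needed. The statistical price is more suspensions at an acceptable dose: acceptance at a 25% true rate goes from 0.86 to about 0.80-0.86, lowest when onset is early. The text should also say that the gain is small if accrual is fast and onset is late.
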